Appendix 5. Categorical Classes for Vital Signs of Clinical Concern

Categories for Vital Signs

Systolic BP (mm Hg)	min. < 90
---------------------	-----------

Systolic BP (mm Hg) change from baseline	max, decrease ≤ 30	max, increase ≤ 30
Diasstolic BP (mm Hg)	min. < 50	
Diastolic BP (mm Hg) change from baseline	max, decrease ≤ 20	max, increase ≤ 20
Supine pulse rate (bpm)	min. < 40	max. > 120

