5.6.3. Vital Signs

Absolute values and changes from baseline in supine systolic and diastolic blood pressure, oral temperature, and pulse rate will be summarized by treatment in accordance with the sponsor reporting standards. Tables will be paged by parameter. Baseline is as defined in [Section 2.4](#).

Mean changes from baseline for supine systolic and diastolic blood pressure, oral temperature, and pulse rate for each treatment will be plotted against time post-dose. On each plot there will be 1 line for each treatment. Corresponding individual plots of changes from baseline will also be produced for each treatment.

Maximum absolute values and changes from baseline for vital signs will also be summarized descriptively by treatment, using categories as defined in [Appendix 5](#). Numbers and percentages of subjects meeting the categorical criteria will be provided. All planned and unplanned post-dose timepoints will be counted in these categorical summaries. All values meeting the criteria of potential clinical concern will be listed.

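### SAP Appendix 5 prints the four blood pressure change categories with the inequality pointing at small changes, so no category identifies a large rise

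*SAP*

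**What the plan says.** SAP Appendix 5 is titled "Categorical Classes for Vital Signs of Clinical Concern". Its entries, in mm Hg or beats per minute, are:

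| Parameter | Low or fall | High or rise |
|---|---|---|
| Systolic BP, absolute | minimum < 90 | none |
| Systolic BP, change | "max, decrease ≤ 30" | "max, increase ≤ 30" |
| Diastolic BP, absolute | minimum < 50 | none |
| Diastolic BP, change | "max, decrease ≤ 20" | "max, increase ≤ 20" |
| Supine pulse rate | minimum < 40 | maximum > 120 |

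SAP Section 5.6.3 puts the table to use: "Maximum absolute values and changes from baseline for vital signs will also be summarized descriptively by treatment, using categories as defined in" Appendix 5. It asks for the number and percentage of participants meeting the criteria, with planned and unplanned post-dose readings both counted, and adds "All values meeting the criteria of potential clinical concern will be listed". No other section of the SAP or protocol gives different cut-offs for blood pressure change or states the direction.

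**The concern.** A category of clinical concern should pick out values far from baseline. The absolute blood pressure and pulse entries do so, but the four change entries do the opposite: they admit small changes and exclude large ones.

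A program written from this table would place most children in a concern category and leave the flag off the readings the listing exists to show. Safety is a primary objective of the study, and change from baseline in vital signs is a secondary safety endpoint. The gap is widest for rises, because neither blood pressure has an upper absolute limit to act as a backstop.

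**Working it through.** There is no planned figure to reproduce: the SAP states no hypotheses and gives no expected counts for this table. The check has three parts.

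**1. Apply the printed entries to single readings.** Changes are read by direction, from an assumed baseline of 100/62 mm Hg.

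| Change (mm Hg) | Printed entries met | Entries met with the four inequalities reversed |
|---|---|---|
| Systolic +2, +5, +20 | rise | none |
| Systolic +30 | rise | rise |
| Systolic +31, +45, +60 | none | rise |
| Systolic −31, −45 | absolute minimum only (69 and 55 are < 90) | absolute minimum and fall |
| Diastolic +2, +5 | rise | none |
| Diastolic +20 | rise | rise |
| Diastolic +21, +30, +45 | none | rise |

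The catch on falls depends on baseline: from 125, a systolic fall of 31 ends at 94 and meets no printed entry. If a fall is coded as a signed number, a rise of 45 is a fall of −45 and meets the ≤ 30 fall entry. Almost every other reading meets it too, so this does not identify a rise.

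**2. Can a lost symbol explain the text?** A dropped minus sign (change ≤ −30 or ≤ −20) would repair the two fall entries. No sign convention repairs the two rise entries. A ≥ misread as ≤ would repair all four, but both symbols appear intact in the SAP objectives table (Section 1.1), ≥ appears again in Sections 4.3.1 and 5.2.11, and < and > appear correctly within Appendix 5.

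**3. Illustrative size per child.** The documents give no SD for blood pressure change, so these inputs are assumptions except where noted:

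- K = 8 post-baseline readings (Months 3 to 24, every 3 months, from the protocol Schedule of Activities);
- normally distributed change with mean 0 and between-visit correlation ρ = 0.5;
- SD 8–15 mm Hg systolic and 6–12 mm Hg diastolic;
- 63 children (the planned number), all attending every visit.

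The probability that a child's largest rise is at most c is

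P(max ≤ c) = ∫ φ(z) · Φ((c/SD − √ρ·z)/√(1−ρ))^8 dz.

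| | SD | Meets printed entry | Exceeds cut-off | Of 63: meets / exceeds |
|---|---|---|---|---|
| Systolic, c = 30 | 8 | 0.9993 | 0.0007 | 63.0 / 0.0 |
| | 10 | 0.9909 | 0.0091 | 62.4 / 0.6 |
| | 12 | 0.9627 | 0.0373 | 60.7 / 2.3 |
| | 15 | 0.8843 | 0.1157 | 55.7 / 7.3 |
| Diastolic, c = 20 | 6 | 0.9969 | 0.0031 | 62.8 / 0.2 |
| | 8 | 0.9627 | 0.0373 | 60.7 / 2.3 |
| | 10 | 0.8843 | 0.1157 | 55.7 / 7.3 |
| | 12 | 0.7885 | 0.2115 | 49.7 / 13.3 |

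By symmetry the same figures apply to the fall entries.

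Sensitivity: at diastolic SD 12, the printed share is 0.676, 0.789 and 0.838 for ρ = 0, 0.5 and 0.7. With a mean rise of 5 mm Hg instead of 0, the share exceeding the cut-off at the largest SD goes from 11.6% to 21.2% (systolic) and from 21.1% to 38.1% (diastolic). The printed entry still takes in most children.

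A simulation of 400,000 children (ρ = 0.5) shows that, of those whose largest rise exceeds the cut-off, 98.8–100% still meet the printed fall entry. Such a child would usually appear in the table, but for an unremarkable reading.

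**The case against.** The strongest objection is that everything rests on one symbol in a table that did not convert cleanly: the first systolic row is separated from the rest. Comparison symbols are also inconsistent elsewhere; the PK age range has > 2 in SAP Section 2.2 and ≥ 2 in Section 5.2.11. This stands as a reason to check the PDF before acting. It does not outweigh the agreement of all four entries or the survival of ≥ elsewhere in the SAP.

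Second, the loss is partial. If the table counts children with a largest change of at most 30, the number above 30 is the complement among those assessed. A child with an extreme rise will usually be listed through another reading. Section 5.6.3 also plans descriptive change summaries and mean plots, and it states "Corresponding individual plots of changes from baseline will also be produced for each treatment". Clinically significant vital-sign changes are adverse events under the protocol's Appendix 3, and an internal committee reviews safety. A table that puts nearly every child in a concern category would probably be noticed. All of this is fair and limits the importance of the point. It does not make the printed rule usable, and the targeted listing is still lost.

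Third, the size rests on assumed SDs, correlation and mean change, and unplanned readings are ignored. That also stands; the figures are illustrative. The direction of the error follows from the table alone.

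Last, the complement of ≤ 30 is > 30, not ≥ 30. For whole-number readings at SD 15 these give about 10.8% and 12.4%. The documents do not say which was meant, so the sponsor should confirm the boundary.

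**Conclusion.** The concern holds. As printed, the four blood pressure change entries select small changes, contrary to the table's title and its other rows, and Section 5.6.3 makes them operative for the counts and the listing. No entry identifies a large rise; a large fall is caught only when the absolute value drops below 90 systolic or 50 diastolic.

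Under the stated assumptions, each printed category takes in 88.4–99.9% of children (systolic) or 78.9–99.7% (diastolic), against 0.1–11.6% and 0.3–21.1% beyond the cut-off. What is lost is the flag on the extreme reading in this one summary and its listing; no efficacy or adverse event analysis depends on it. This should be corrected before the tables are programmed. Confidence is moderate, because the symbol has yet to be confirmed in the source PDF.

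**What to change.** Check the symbol in the four change cells of SAP Appendix 5 against the source PDF. If it is as printed, reverse the inequality in all four so that they select changes at or beyond the SAP's own cut-offs: ≥ 30 mm Hg systolic and ≥ 20 mm Hg diastolic, for rises and falls. The sponsor should confirm the direction, the cut-offs and the boundary (≥ or >) against its reporting standards, and state whether an upper absolute blood pressure category was intended.

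The cost is four symbols in one appendix and the matching table and listing program. No new data are needed.

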Appendix 6. List of Abbreviations

	Term
Abs	absolute
AE	adverse event
ANOVA	analysis of variance
BLQ	below the limit of quantitation
BP	blood pressure
CDARS	Clinical Data Analysis and Reporting System (of US Food and Drug Administration)
CI	confidence interval
CSR	clinical study report
DMC	data monitoring committee
ECG	electrocardiogram
E-DMC	external data monitoring committee
FAS	full analysis set
LLOQ	lower limit of quantitation
LOCF	last observation carried forward

	Term
LOD	limit of detection
LS	least-squares
LSM	least-squares mean
MedDRA	Medical Dictionary for Regulatory Activities
MMRM	mixed-effects model with repeated measures
N/A	not applicable
CCI	
PK	pharmacokinetic(s)
PP	per-protocol
PPAS	per-protocol analysis set
PR interval	time from the beginning of the P wave to the beginning of QRS complex
PT	preferred term
QRS	a combination of the Q wave, R wave and S wave
QTc	corrected QT
QTcB	corrected QT (Bazzett method)
QTcF	corrected QT (Fridericia method)
RR	respiratory rate
SAE	serious adverse event
SAP	statistical analysis plan
SD	standard deviation
SGS	Statistical Guidance Standards
SOP	standard operating procedure
